8.3 HIV Sexual Risk Behavior

HIV sexual risk behavior outcomes will be assessed at all time points throughout the study, and will be operationalized dichotomously (e.g., incident STI via biomarker testing), as a counted variable (e.g., number of days/times engaged in CAI in the past 30 days), and as a continuous variable (e.g., a HIV risk severity index generated from multiple factor-analyzed items). Power calculations for engagement in HIV sexual risk behaviors assume a 65% probability of engagement during the pre-intervention period for participants in the DD arm (equivalent to ~2:1 odds of engagement). Multivariable inferential analyses of dichotomous outcomes will take the form of GLMs employing the Bernoulli family and logit link function; counted outcomes will be analyzed with GLMs employing the Poisson-log or negative binomial link functions as distributional patterns dictate (note: if data evidence an over-representation of zeros or an overdispersion of variance, zero-inflated Poisson and/or negative binomial analyses may be substituted); continuous outcomes will be analyzed using GLMs employing the identity link and Gaussian family functions and assume a single covariate unless otherwise stated (note: iteratively reweighted, bootstrapped, or jack-knifed estimation procedures may be used in Gaussian models if sensitivity analyses indicate undue influence from outliers). Mixed effects GLM models are considered the best linear unbiased estimators for repeated measures data employing non-parametric and/or limited dependent variables. All power calculations are premised on tests of association across two time points (e.g., baseline with app completion; app completion with brick-and-mortar program completion), providing the most conservative estimate of minimum detectable effect (MDE) size estimations; all power calculations assume $\alpha \leq 0.05$ (two-tailed), and $1 - \beta = 0.80$.

Table 2: Instruments, Targets, Variable Operationalizations, and Minimum Detectable Effects

Table 2: Instruments, Targets, Variable Operationalizations, and Minimum Detectable Effects (1 - β = 0.80; α = 0.05, two-tailed)

Instrument	Target	Variable Operationalizations			Power-- Minimum Detectable Effects		
		Dichotomous (Di)	Count (Cu)	Continuous (Co)	Model 1— RCT (Aim 1a; n=150/n=150)	Model 2— Tx Effects (Aim 1b; N = 300)	Model 3— Matched Comparison (Aim 1c; N = 300/N ~ 600)
DSM-5 (MA)	Diagnosis of MA Use Disorder	Presence/Absence of MA Use Disorder	# of Diagnostic Criteria Endorsed	N/A	Potential Statistical Controls; Exploratory Sub-Group Analyses		
URICA	Stage of Change/ Readiness for Change	Above/Below "Action" Stage	N/A	URICA Score(s)	Potential Statistical Controls; Exploratory Sub-Group Analyses		
Admissions & Follow-up Form	Sociodemographics; HIV Status and Tx History, Barriers & Facilitators	Sexual Identity; HIV Status; Linked/Unlinked; Housing Insecurity	Prior Drug Treatment Episodes; Symptomology	Age; Income	Potential Statistical Controls; HIV-Related Sub-Group Analyses; Barrier/Facilitator Moderator Analyses		
	HIV Prevention or Care Continuum ^a	HIV Test; PrEP Uptake; Advance along HIV Prevention or Care Continuum	Prevention or Care Continua Steps Completed	N/A	Di: OR = 1.97; Cu: IRR = 1.51; Co: f^2 = 0.03	Di: OR = 1.61; Cu: IRR = 1.35	Di: OR = 1.52; Cu: IRR = 1.30; Co: f^2 = 0.01
Biomarker Tests (UA, VL, DBS, HIV/STI)	MA Use, HIV Prevention/Care Continuum Outcomes, Sexual Risk Behavior	Incident STI /Incident HIV	Log reductions in HIV VL; DBS Analysis of PrEP	Treatment Effectiveness Score	Variable	Variable	Variable
Substance Use Freq.	MA Use	Use/Non-use	Days of Use	N/A	Di: OR = 0.48; Cu: IRR = 0.85; Co: f^2 = 0.03	Di: OR = 0.59; Cu: IRR = 0.89; Co: f^2 = 0.01	Di: OR = 0.62; Cu: IRR = 0.90; Co: f^2 = 0.01
BQA	HIV Sexual Risk Behavior	CAI ^b	# CAI ^b Episodes	HIV Sexual Risk Scale	Di: OR = 0.52; Cu: IRR = 0.78; Co: f^2 = 0.03	Di: OR = 0.63; Cu: IRR = 0.85; Co: f^2 = 0.01	Di: OR = 0.66; Cu: IRR = 0.87; Co: f^2 = 0.01
Locator	Contact Information						

^aHIV Prevention Continuum (HIV testing and PrEP/PEP uptake) and HIV Care Continuum (link, ART adherence, virological suppression).

^bCAI: Condomless Anal Intercourse includes both receptive and insertive anal intercourse, and will be assessed by partner type (e.g., main, casual, exchange)

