1.0 STUDY OBJECTIVES

1.1 Specific Aims

- 1.1.1 Specific Aim 1a: Conduct a RCT to evaluate reductions of methamphetamine use and HIV sexual risk behaviors, and increased advancement along the HIV Prevention or Care Continuum using a two-arm RCT to determine intervention effects through comparison of the Immediate Delivery [ID] (n=150) and Delayed Delivery [DD] (n=150) arms.
- 1.1.2 Specific Aim 1b: Evaluate reductions in methamphetamine use and HIV sexual risk behaviors, and increased advancement along the HIV Prevention or Care Continuum using an observed treatment effects analysis powered for prospective sub-group analyses to compare longitudinal pre/post data from the pooled ID and DD arms (n=300);
- 1.1.3 Specific Aim 1c: Evaluate reductions in methamphetamine use and HIV sexual risk behaviors, and increased advancement along the HIV Prevention or Care Continuum using a two-arm historical matched comparison design to evaluate the outcomes of the *Getting Off* app (ID+DD; n=300) relative to a matched sample of participants having previously attended the brick-and-mortar group-based *Getting Off* intervention (n~600; total n=900).

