8.0 STATISTICAL ANALYSES

8.1 General Analytical Approach

All primary outcomes are operationalized and assessed in at least two discrete ways, increasing accuracy of measurements, reducing concerns of fully missing data, and allowing for post-hoc comparisons of concurrent validity across assessment modalities (see Table 2 for all outcome operationalizations). Descriptive statistics will be calculated and provided for all outcomes, with specific metrics chosen based on the distributional properties of each variable (e.g., counts and percentages for nominal variables; means and standard deviations for parametric continuous variables; ranges and medians for non-parametric continuous variables). Diagnostic (i.e., DSM-5), psychosocial (e.g., URICA), barriers and facilitators (e.g., housing insecurity, lack of transportation), and/or sociodemographic variables will be tested for significant association with study outcomes (i.e., advancement through the HIV Prevention or Care Continuum, methamphetamine use, HIV sexual risk behaviors), with specific tests of association chosen based on the distributional properties of the outcome variables in question. All variables demonstrating significant statistical association with one or more of the study outcomes will be included as statistical covariates in all multivariate outcome analyses associated with Specific Aims 1a-1c, and will additionally be included in exploratory sub-group analyses to test for moderating effects on treatment response and/or contingent effects among subsets of participants. Primary outcome analyses for Specific Aims 1a, 1b, and 1c will be carried out using mixed effects Generalized Linear Model (GLM) equations.

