8.2 Advancement through the HIV Prevention or Care Continuum

Advancement through the HIV Prevention or Care Continuum will be assessed at all time points throughout the study, and will be operationalized dichotomously (i.e., yes/no achievement of one of the steps on either the HIV Prevention or Care Continuum; e.g., viral suppression), and

as a counted variable (e.g., consecutive DBS results indicating successful PrEP adherence). Power calculations related to advancement through either continuum will assume a 30% probability of achievement of at least one of the steps on either the HIV Prevention or Care Continuum (equivalent to ~1:2 odds of advancement). Methamphetamine use outcomes will be assessed repeatedly (i.e., at all time points) and will be operationalized dichotomously (e.g., methamphetamine-metabolite-free urine sample), as a counted variable (i.e., number of methamphetamine-metabolite-free urine samples provided), and as a continuous variable (i.e., Treatment Effectiveness Score [total number of methamphetamine-metabolite-free sample divided by total samples possible]). Power calculations related to methamphetamine use outcomes assume an 80% probability of methamphetamine use during the pre-intervention period for participants in the DD arm (equivalent to 4:1 odds of use).

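### Section 8.3 permits zero-inflated Poisson for overdispersion alone and does not say which parameter of a zero-inflated model is the treatment effect

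*Combined protocol and SAP*

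**What the plan says.** Section 8.3 sets the default for counts: "counted outcomes will be analyzed with GLMs employing the Poisson-log or negative binomial link functions as distributional patterns dictate". A parenthetical note then adds: "if data evidence an over-representation of zeros or an overdispersion of variance, zero-inflated Poisson and/or negative binomial analyses may be substituted". The two triggers are joined by *or*, neither is tied to a model, and the substitution is optional. The last words can mean ordinary or zero-inflated negative binomial.

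Section 8.1 requires a repeated-measures form: "Primary outcome analyses for Specific Aims 1a, 1b, and 1c will be carried out using mixed effects Generalized Linear Model (GLM) equations". It also has each primary outcome operationalized in at least two ways, so the counts are not merely exploratory.

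For methamphetamine use in Aim 1a, Table 2 gives minimum detectable effects (MDEs) of "Di: OR = 0.48; Cu: IRR = 0.85; Co: f^2 = 0.03", with Use/Non-use as the dichotomous outcome and Days of Use as the count. Section 8.2 says the power calculations "assume an 80% probability of methamphetamine use during the pre-intervention period for participants in the DD arm (equivalent to 4:1 odds of use".

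The documents give no mean or variance for days of use, no robust-variance rule for counts (the bootstrap and jack-knife remark in Section 8.3 concerns Gaussian models), no model-selection rule, and no statement of which part of a zero-inflated model carries the arm effect.

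**The concern.** There are two separate faults.

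1. **Error rate.** Zero-inflated Poisson adds a point mass at zero but keeps a Poisson variance for everyone else. If days of use vary more than that among users, the count-part standard error is too small and the test rejects too often.
2. **Estimand.** In a standard zero-inflated model the count-part IRR compares mean counts outside the excess-zero class. An effect that turns users into abstainers goes mostly to the zero part. The IRR can then sit near 1 while total days of use fall.

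The trial is non-blinded (Section 9.1), and the note lets the model be chosen from the observed outcome distribution. One dataset could give a spuriously significant zero-inflated Poisson IRR, a null count-part IRR or an overall rate ratio, all labelled IRR.

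**Working it through.** **Inputs from the documents.** 150 per arm (Section 1.1); two-sided alpha 0.05 and power 0.80 (Table 2); 80% use in the delayed arm, odds 4 (Section 8.2); OR 0.48 and IRR 0.85 for methamphetamine use (Table 2, Section 9.1); a 30-day recall window (Section 6.6.2.4), so days of use run from 0 to 30.

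**Assumed, because the documents are silent.** The variance/mean ratio (VMR) of days among users, the shape of that distribution (beta-binomial or negative binomial), and a within-person correlation of 0.5-0.8.

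**Step 1: reproduce the plan's figures.** No count base rate is stated. Taking the stated odds of 4 as the control mean, a two-group Poisson comparison with N = 300 gives

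power = Φ{(|ln 0.85| × √(300 × 4) − 1.96 × 2) / √(2 + 2/0.85)} = Φ{(0.1625 × 34.64 − 3.92) / 2.086} = Φ(0.82) = 0.794.

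A Wald version gives 0.770 at IRR 0.85 (MDE 0.844). With base rates 2 and 0.5 it gives 0.813 at the sexual-risk IRR of 0.78 and 0.791 at the continuum IRR of 1.51. No one variant fits all three, but each is met by a standard formula for a single Poisson rate ratio. For OR 0.48 from 80%, a two-proportion calculation gives power 0.796.

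**Step 2: zero-inflated Poisson with no arm effect, one time point, model-based SEs.** If the true variance is VMR times the assumed one, the rejection rate is about 2Φ(−1.96/√VMR).

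| VMR among users | Formula | Simulation (150 v 150, 80% users) |
|---|---|---|
| about 1 | 5% | 4.8% |
| 1.4 | 10% | 10% |
| 2.0-2.5 | 17-22% | 17-22% |
| 3.8-4.5 | 32-36% | 31-37% |
| 5-7 | 38-46% | 39-47% |

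To show which VMRs are possible: days spread evenly over 1-30 have mean 15.5 and variance (30² − 1)/12 = 74.9, so VMR 4.8. Spread over 1-15, the mean is 8 and the variance 18.7, so VMR 2.3. Zero-inflated Poisson with robust SEs rejected in 4.6-6.3% of runs.

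**Step 3: closer to the planned mixed model.** With a random intercept (baseline plus 1 month), rejection was 25%, 20% and 10% in three settings with VMR about 4.4 (600 runs each), and 9% and 4% with VMR about 2.4 (200 runs each).

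**Step 4: abstinence-only effect at the plan's own OR.** Treated odds are 4 × 0.48 = 1.92, so use is 1.92/2.92 = 65.75%. If users' mean days m do not change, the overall mean ratio is (0.6575 × m)/(0.80 × m) = 0.822, beyond the 0.85 MDE. The count part compares m with m. In simulation the zero-inflated Poisson count-part IRR was 1.00 and was rejected in about 4-5% of runs with robust SEs; ordinary negative binomial gave 0.81-0.82. Zero-inflated negative binomial gave 1.00 at users' mean 8 and about 0.95 at mean 5, where only 119 of 300 fits were usable. The Use/Non-use test rejected in 78-84% of runs.

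The same arithmetic for condomless anal intercourse, from 65% with OR 0.52: odds 1.857 × 0.52 = 0.966, so 49.1%. The ratio is 0.491/0.65 = 0.756, beyond the 0.78 MDE.

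**Step 5: test the replacement.** With user days of assumed mean/SD 8/5, 10/8 and 15/9, a ratio of overall means with robust SEs rejected in about 4-6% of null runs and had 31-47% power for the Step 4 effect. Negative binomial with model-based SEs rejected in 0-4% of null runs and had 12-24% power. The robust variance therefore has to be part of the replacement.

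**The case against.** Negative binomial, a standard answer to overdispersion, is already in the default rule and is named again in the note. The note can fairly be read as zero-inflated Poisson for excess zeros and negative binomial for overdispersion. That stands: a reader might infer that the plan intends to treat overdispersion with zero-inflated Poisson, but the text only permits it.

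A reader might also attach a false-positive rate of 30-43% to this trial. The documents do not support a single figure. That range needs a VMR of about 3.6-6.2, one time point and model-based SEs. The planned random intercept lowers the rate, and robust SEs bring it to about 5%.

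Nor is the abstinence effect lost to the trial. Use/Non-use is a separate planned outcome with about 80% power for it, and a zero-inflated fit can show it in the zero part. It would also be too broad to say that every zero-inflated model hides it: a marginalized model, or a mean ratio built from both parts, keeps it, and zero-inflated negative binomial at low means keeps some.

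Finally, Section 8.2 describes the counted methamphetamine outcome as metabolite-free urine samples. The simulations cover only Table 2's days of use.

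What remains is that the note ties neither trigger to a model, gives no selection rule and leaves the count effect undefined.

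**Conclusion.** The point holds as a should-fix. The note allows an analysis whose type I error exceeds 5% when users' counts are overdispersed and SEs are model-based: about 10% at VMR 1.4, 17-22% at 2-2.5 and 31-47% at 4-7 for one time point. With a random intercept the range is 4-25%, so inflation is present in most of the settings tried but not all. These sizes rest on the assumed VMR, distribution and correlation.

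The estimand fault needs no VMR. At OR 0.48 from 80% use, with users' mean unchanged, the overall ratio is 0.822 and the count-part IRR of a standard zero-inflated model is about 1. The counted outcome would then not estimate the single rate ratio to which Table 2's IRR MDEs refer, and it could appear to contradict Use/Non-use.

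**What to change.** Replace the note in Section 8.3 with:

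> For counted outcomes the treatment effect is the ratio of overall mean counts, zeros included, from a log-link Poisson or negative binomial repeated-measures model with robust (participant-clustered) standard errors; the model is fixed before outcome data are compared by arm. Zero-inflated Poisson is not used for overdispersion. Any zero-inflated model is a sensitivity analysis, reporting the marginal ratio of means with the zero part shown separately.

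The cost is one paragraph of text. The downside is some loss of efficiency if the app changes only the count among continuing users. The change corrects the error rate and the estimand; it does not give the count 80% power for an abstinence-only effect (31-47% in the settings tried).

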2.0 INTRODUCTION

2.1 Rationale

Methamphetamine use among MSM is associated with increased rates of HIV prevalence and transmission, as well as substandard advancement along the HIV Prevention and Care Continua. Methamphetamine use among MSM is deeply integrated into socio-sexual networks including the use of smartphone apps and websites to find sexual partners. Given the growth of mobile health technology, it is no longer necessary or reasonable to limit methamphetamine treatment options to physical sites, clustered in urban areas, and administered using generic, non-tailored content. The project builds upon the established efficacy of our manualized methamphetamine-use treatment intervention, “*Getting Off: A Behavioral Treatment Intervention for Gay and Bisexual Male Methamphetamine Users*,” and the highly promising findings from the successful Stage I proof-of-concept study, to complete translation of *Getting Off* into a cross-platform (iOS and Android) app and assess the app’s efficacy *and* non-inferiority in a scientifically rigorous randomized trial. The *Getting Off* app, like the group-based intervention before it, will use the principles of Cognitive Behavioral Theory and Stages of Change to help MSM reduce or eliminate methamphetamine use and HIV sexual risk behaviors, and increase advancement along the HIV Prevention or Care Continuum (including uptake of HIV testing, pre-, and post-exposure prophylaxis [PEP/PrEP] and PrEP adherence and persistence for those who are HIV negative; ART uptake and adherence for those who are HIV positive).

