You'll have opportunities during this program to look at these areas of your life again so you can see the areas where you're making improvements and the areas you may need to focus more energy on.

Session 1: Calendars and Dots Around the Clock

Top left: Each user can personalize his avatar by choosing facial structure, skin tone, hair, facial hair, clothing, and background. Bottom left: An example of the translation from manual to app. Right: Screenshots showing how the *Getting Off* app provides information on the stages of recovery from methamphetamine use, a risk calculator for methamphetamine use and high-risk sexual behaviors, a reflective exercise on disassociating sexual behaviors from methamphetamine use, and a goal-setting exercise to increase self-efficacy.

A feasibility pilot test was conducted on the original eight sessions. Participants (N=15) in the feasibility pilot test were 40% Caucasian/White, 33% African American/Black, and 27% Hispanic/Latino; 73% identified as gay and 27% identified as bisexual. Ages ranged from 25-55 years (Mean=43; SD=9); 67% were HIV positive. Most (87%) met criteria for DSM-5 methamphetamine use disorder (60% severe). In the past 30 days, 80% reported methamphetamine use, 67% reported sex with a casual male partner (Mean=1.7; SD=0.9), and 25% reported sex with an anonymous male partner (Mean=2.5; SD=2.4). Pilot test participants were identified as similar to prospective app users; 53% (n=8) were out-of-treatment, current methamphetamine users and 47% (n=7) were methamphetamine users who had recently sought treatment for their methamphetamine use with no more than six months of recovery. Backend app user data indicated that average progression rates (i.e., how much of a session the participant completed) ranged from 62% (Recall) to 91% (Redefine), and the median completion rate for every session was 100% across all 15 participants. Twelve (80%) participants finished all sessions and completed both the initial and closing self-assessments; on average these participants reported improvements in self-esteem, social life, family life, drug

use, and alcohol use. Follow-up interviews (n=14; 93%) indicated mean participant satisfaction rating was high (8.5/10).

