6.6.3. Biomarker Assessments

6.6.3.1 HIV-antibody Test. HIV-negative and status unknown participants will receive a fingerstick DBS test at 3-month intervals, as recommended by the CDC for high-risk individuals. Participants who show documentation of HIV-positive serostatus are not given a HIV-antibody test. If the test is reactive, then the participant will be presumed positive for HIV antibodies and referred for additional evaluation and treatment. If the DBS sample is rejected by the lab or if the quantity of blood is insufficient, participants will be asked to come to the study site to have the test performed via fingerstick blood test using the INSTI HIV 1/HIV 2 antibody test, or to provide a copy of recent results (within 3 months) from their medical provider. Conducted at baseline and at the 3-, 6-, and 9-month follow-up time points (if previously tested HIV-negative or status is unknown).

6.6.3.2 STI Testing. Participants will be tested for urinary N. gonorrhoea and Chlamydia, pharyngeal and rectal swabs will be taken for N. gonorrhoea and Chlamydia, and syphilis will be tested by fingerstick DBS. Positive STI results will be reported per state guidelines and will be immediately referred to care. If the DBS sample is rejected by the lab or if the quantity of blood is insufficient, participants will be asked to come to the study site to have the test performed via intravenous blood draw or to provide a copy of recent results (within 3 months) from their medical provider. Conducted at baseline and at the 3-, 6-, and 9-month follow-up time points.

6.6.3.3 Virologic Control for HIV-positive Participants. As indicated by an undetectable HIV-1 level via intravenous blood draw, which has a threshold for undetectability = <30 copies/mL will be performed by Foundation Laboratory. Viral load testing through Foundation Laboratory may be bypassed if participants can provide recent (within 3 months) lab results from their medical provider. Conducted at baseline and at the 3-, 6-, and 9-month follow-up time points.

6.6.3.4 Dried Blood Spot (DBS) for HIV-negative Participants who Report PrEP Uptake. A blood sample will be collected and a DBS analysis for intra-erythrocytic TFV-DP will be performed by Molecular Testing Labs. Conducted at baseline and at the 3-, 6-, and 9-month follow-up time points.

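### Table 2 gives HIV Test and PrEP Uptake the minimum detectable odds ratios of the whole-sample composite, but only HIV-negative or status-unknown men can reach those two outcomes

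*Combined protocol and SAP*

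**What the plan says.** Table 2 (section 8.3) has a row for the HIV Prevention or Care Continuum under the Admissions & Follow-up Form. Its dichotomous cell reads "HIV Test; PrEP Uptake; Advance along HIV Prevention or Care Continuum". The Aim 1a cell of the same row reads "Di: OR = 1.97; Cu: IRR = 1.51; Co: f^2 = 0.03"; the dichotomous figures for Aims 1b and 1c are OR 1.61 and OR 1.52. The table title sets the conditions, "Minimum Detectable Effects (1 - β = 0.80; α = 0.05, two-tailed", and the column heads set the sample sizes: 150 v 150, 300, and 300 v about 600. The Aim 1a, 1b and 1c power statements in section 9 repeat the odds ratios for continuum outcomes as a group.

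Section 8.2 gives the base rate: the calculations "will assume a 30% probability of achievement of at least one of the steps on either the HIV Prevention or Care Continuum".

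On who can reach which step:
- Footnote a to Table 2 places HIV testing and PrEP/PEP uptake on the Prevention Continuum.
- Section 2.1 divides the steps by serostatus: "PrEP adherence and persistence for those who are HIV negative; ART uptake and adherence for those who are HIV positive".
- Section 6.6.3.1 adds: "Participants who show documentation of HIV-positive serostatus are not given a HIV-antibody test".
- Section 6.4 balances randomisation on HIV serostatus, so both groups are enrolled.

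No planned serostatus split is given. The only figure is from the 15-man feasibility pilot in section 2.2.5: "67% were HIV positive". Section 1.1.2 describes Aim 1b as powered for subgroup work, but no MDE by serostatus appears.

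**The concern.** The composite is open to every participant, because each man is on one continuum or the other. HIV testing and PrEP uptake are not. A single MDE for all three outcomes carries the full sample size, and a base rate defined for the composite, over to two outcomes that only part of the sample can achieve. Nothing in the row limits the figure to the composite. Elsewhere the table does avoid a single figure: the biomarker row is marked as variable.

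At stake is how results on these two outcomes are read. A reader relying on Table 2 would take the trial to have 80% power against OR 1.97 for PrEP uptake, and would give a null result more weight than it deserves.

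**Working it through.** **Inputs.** Two-sided α 0.05 and power 0.80 (Table 2 title). Base rate p1 = 0.30 (section 8.2). Sample sizes 150/150, 300/300 and 300/600 (Table 2 column heads). Aim 1b is treated as 300 v 300 independent observations. A paired calculation would need a within-person correlation that the documents do not give.

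**Formulas.** p2 = p1·OR / (1 − p1 + p1·OR). For equal groups of n, with p̄ the mean of p1 and p2:

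power = Φ{ [ |p2 − p1| − 1.96·√(2p̄(1 − p̄)/n) ] / √[ (p1(1 − p1) + p2(1 − p2))/n ] }

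For Aim 1c the same test is used with unequal groups. The MDE is the OR at which power equals 0.80.

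**Step 1: the plan's own figures.** At OR 1.97, p2 = 0.591/1.291 = 0.4578 and p̄ = 0.3789. With n = 150 the two standard errors are 0.0560 and 0.0553, so power = Φ[(0.1578 − 0.1098)/0.0553] = Φ(0.868) = 80.7%.

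| Aim | n | Printed OR | Power at printed OR | Recomputed MDE |
|---|---|---|---|---|
| 1a | 150/150 | 1.97 | 80.7% | 1.96 |
| 1b | 300/300 | 1.61 | 79.3% | 1.62 |
| 1c | 300/600 | 1.52 | 79.9% | 1.52 |

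A Wald test on the log odds ratio gives 80.0% for Aim 1a at OR 1.97. The printed figures therefore use every participant and the composite's 30% rate.

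**Step 2: men who can achieve the step.** The serostatus split is an assumption, shown as a range. Eligible men per arm = 150 × (1 − HIV-positive share): 49 (49.5 rounded down), 75 and 105. With p1 = 0.30 and OR 1.97:

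- n = 49: Φ[(0.1578 − 0.1921)/0.0967] = Φ(−0.355) = 36%
- n = 75: Φ[(0.1578 − 0.1553)/0.0782] = Φ(0.032) = 51%
- n = 105: Φ[(0.1578 − 0.1312)/0.0661] = Φ(0.402) = 66%

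For Aims 1b and 1c the numbers are cut in the same proportion: 98, 150 or 210 for Aim 1b, and 98/196, 150/300 or 210/420 for Aim 1c, with the 30% rate placed in the historical group.

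| Assumed HIV-positive share | Aim 1a power at OR 1.97 | Aim 1a MDE (printed 1.97) | Aim 1b MDE (printed 1.61) | Aim 1c MDE (printed 1.52) |
|---|---|---|---|---|
| 67% | 36% | 3.19 | 2.28 | 2.04 |
| 50% | 51% | 2.56 | 1.96 | 1.79 |
| 30% | 66% | 2.22 | 1.77 | 1.64 |

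Even at 10% HIV-positive (135 per arm), Aim 1a power is 76%.

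**Step 3: can another base rate restore 80%?** Power at OR 1.97 is highest at a base rate of about 0.42. There it is 38%, 54% and 68% for 49, 75 and 105 per arm, and 79% for 135. Reaching 80% at that best rate takes at least 139 eligible men of 150 per arm (139/150 = 93%). At the 30% rate it takes 148.

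**Step 4: can all 150 per arm be kept, with HIV-positive men scored as no?** With half the men eligible, the whole-arm rates are 0.30 × 0.50 = 0.150 and 0.4578 × 0.50 = 0.229. The odds ratio shrinks from 1.97 to 1.68 and power is 41%. With 33% eligible power is 27%, and with 67% it is 56%.

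**The case against.** The best defence is that section 8.2 says what was sized: achievement of at least one step on either continuum. Every man can reach that, and the printed odds ratios are correct for it. On this reading the other two entries in the cell are alternative codings, the MDE belongs to the row's target, and no prose claims 80% power for PrEP uptake alone. This stands as far as it goes: nothing is miscalculated. But the table prints the MDE against all three outcomes without a caveat, and section 9 repeats it for continuum outcomes in the plural. If the composite alone is meant, the table should say so.

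The size is also open to challenge. The pilot's 67% is 10 of 15 men (exact 95% interval about 38% to 88%), and the 50% and 30% shares are illustrative. That limits how firmly any one row of the table can be quoted, but not the direction of the loss.

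Section 6.6.3.1 concerns the study's own antibody test, whereas this row is the self-report form. It supports the point only indirectly; section 2.1 and footnote a carry more weight.

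Three stronger readings are tempting and are not supported:
- A reader might infer that no single step can have a base rate above 30%. That is true only over all men. Among eligible men the rate could reach 0.30/0.50 = 60% if half are eligible. Step 3 therefore searches over base rates.
- A reader might assume a much lower base rate for PrEP uptake and report a still larger MDE. The documents give no such rate.
- A reader might extend the criticism to viral suppression. It enters this row only through footnote a, and Table 2 lists viral load in the biomarker row, where no fixed MDE is stated.

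**Conclusion.** Wrong as written, of moderate weight. OR 1.97 / 1.61 / 1.52 at 80% power is sound for the composite and should stay there. It does not hold for HIV Test or PrEP Uptake once the HIV-positive share is more than about 7% (11 of 150 per arm), whatever the base rate, on the Aim 1a calculation. Over an assumed 67% to 30% HIV-positive, Aim 1a power at OR 1.97 is about 36% to 66%, and the MDE is OR 3.19 to 2.22.

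These sizes rest on an assumed serostatus split, the 30% rate carried over to single steps, independent observations in Aim 1b, and a historical group cut in the same proportion in Aim 1c. Dropout and men already on PrEP at baseline are not counted; both would reduce the numbers further.

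A reader might infer that the trial is too small or that its continuum calculation has failed. The documents do not support that. What needs correcting is the reach of a printed power figure, not the design.

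**What to change.** In Table 2 and in the Aim 1a, 1b and 1c power statements of section 9, state that OR 1.97 / 1.61 / 1.52 apply only to the composite, advancement on either continuum.

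For HIV Test and PrEP Uptake, state that the analysis includes men eligible for that step at baseline (HIV-negative or status unknown). Then either give each its own MDE, from the expected number of eligible men and a stated step-specific base rate, or label it exploratory.

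The cost is wording and a few table lines. Sample size, randomisation and the composite analysis are unchanged. The detectable effects shown for the two single-step outcomes will look less favourable.
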